6.3. Detailed description of study visits

The patients will be observed closely for at least 30 minutes after the administration of study treatment with appropriate medical treatment readily available in case of a rare anaphylactic reaction following the injection.

The patients will be instructed to contact the investigator immediately should they manifest any signs or symptoms they perceive as serious.

6.3.1. Screening phase: Procedures from surgical resection until Visit 1 of the study

6.3.1.1. Visit S1

In addition to whatever other medical procedures are performed, the following (study specific procedures) will be carried out:

Before or after the tumor resection, the patient will be informed about specific aspects of the study (Section 11.1.2) and will sign the informed consent which includes retention and testing of

tumor tissue for MAGE-A3 expression and expression of a predictive gene list associated to treatment. Testing for MAGE-A3 expression will not be completed until informed consent has been obtained regardless of when the tumor resection was performed.

6.3.1.2 Visit S2

This visit will take place after V1, once the results of MAGE-A3 expression testing are known.

The inclusion and exclusion criteria will be evaluated. Only patients who, in the opinion of the investigator, meet all inclusion criteria and none of the exclusion criteria may be included in this study. The following will also be performed at visit S2:

Pregnancy test (for women of child-bearing potential)

When considering the enrollment of females of childbearing potential, please take note of the following definitions:

- Adequate contraception is defined as a contraceptive method with failure rate of less than 1% per year when used consistently and correctly (when applicable, as mentioned in the product label) for example abstinence, combined or progestogen oral contraceptives, injectable progestogen, implants of levonorgestrel, oestrogenic vaginal ring, percutaneous contraceptive patches or intrauterine device (IUD) or intrauterine system (IUS), vasectomy with documented azoospermia of the sole male partner or double barrier method (condom or occlusive cap plus spermicidal agent).

For azoospermia, “documented” refers to the outcome of the investigator's or his/her designee's medical examination of the patient or review of the patient's medical history for study eligibility, as obtained via a verbal interview with the patient or from the patient's medical records.

- Post-menopause: Menopause is the age associated with complete cessation of menstrual cycles, menses, and implies the loss of reproductive potential by ovarian failure. A practical definition accepts menopause after 12 consecutive months without menses with an appropriate clinical profile (for example, at the appropriate age e.g., > 45 years).

- The patient's medical history (inclusive cancer history) will be recorded.

- SAEs related to study participation or concomitant medications are recorded (see Section 8.2).

- Blood sampling for safety haematological and chemical assays (15 ml, as described in Section 6.4.2).

- Neck and chest CT scan, complete abdomen CT scan and pelvic CT scan within 4 weeks preceding treatment.

- Brain MRI scan. If such a scan has been performed up to 4 weeks before treatment, this need not be repeated. Brain CT may be used instead of brain MRI scan if patients are unable to have an MRI, i.e. due to placement of a pacemaker or defibrillator, etc.

- Physical examination

- When the patient is eligible (meets all of the inclusion criteria and none of the exclusion criteria), randomization via the internet will take place (for procedure see Section 5.3.2). A maximum period of 2 weeks is allowed between randomization and the first administration of the study drugs.

6.3.2. Resection procedure

After resection, formalin-fixed paraffin-embedded (FFPE) tumor tissue will be tested for MAGE-A3 expression. A paraffin-embedded tissue block sample of at least 10 mm³ or alternatively 20 unstained slides (19 slides of 10 µm and 1 slide of 5 µm for a total of at least 100 mm² tumor tissue) will be provided to GSK Biologicals or a contracted lab. The laboratory will then extract the RNA from these samples and assess the MAGE-A3 expression by quantitative PCR. If there are several melanoma blocks, it is preferred that 2 of these are sent for determination of MAGE-A3 expression (As described above, a FFPE block of at least 10 mm³ is preferred). The second block will only be tested, in case the first tested is MAGE-A3-negative. The patient will be considered eligible on this criterion, if at least one tested block is MAGE-A3-positive. The gene profile analysis performed by GSK Biologicals or a contracted laboratory will be performed on RNA extracted from fresh tumor tissue obtained from the biopsy and stored in RNA later. Gene expression profiling including the presence or absence of the predictive gene signature will be assessed by an appropriate technology such as qRT-PCR, microarray or IHC on these samples and correlated with the patient's clinical data. Additional gene profiling might be performed in the screening FFPE tumor samples sent for MAGE-A3 screening.

Confirmation of the pathological diagnosis (melanoma stage IV) will be made by the pathologist at MCC using a FFPE section. The extent of sampling is to be entered into the patient's CRF.

6.3.3. Visit 1: First study treatment administration

This visit will take place a maximum of 12 weeks after resection.

The following pre-administration procedures will be performed:

- Physical examination including ECOG performance status and disease assessment.
- Blood sampling for baseline humoral immunity assays will be taken (10 ml, as described in Section 6.4.2).
- Leukapheresis
- Female patients will undergo a urine or serum βHCG pregnancy test (if applicable; see Section 6.3.1.2 for definition of female of childbearing potential). For female patients of

childbearing potential, pregnancy test results must be negative before the first administration of study treatment. For these patients, a pregnancy test will be repeated every 3 months and should be performed at any time during the study if the investigator or patient suspects that pregnancy has occurred while the patient was being treated on protocol therapy.

- Recording of concomitant medications (as described in Section 5.8)
- Recording of potential immune-mediated disease (pIMD).
- SAEs related to study participation or concomitant medications are recorded (see Section 8.2)

The leukapheresis will be performed within 1 week of starting treatment .

Study treatment administration and other procedures will be as follows:

- The patient will receive the randomized study treatment (recMAGE-A3+AS15 ASCI +/- Poly IC:LC given intramuscularly in the deltoid or preferably in the lateral region of the thigh; see Section 5.2) and will thereafter be kept under close observation for at least 30 minutes, with appropriate medical treatment readily available in case of a rare anaphylactic reaction following the injection.
- Any (serious) adverse events that occurred during the study treatment will be recorded.
- For patients who agree, eight green tops of blood totaling 70 mL will be taken on days 1, 3, 7, 14 and 21 after the first and fifth doses of study drugs for assessment of T cell reactivity. Day 21 after the first dose of study drug would be the day of the second injection of study drug. These assays will be performed by [REDACTED]

6.3.4. Visit 2: Second study treatment administration

This visit will take place 3 weeks \pm 4 calendar days after the day of the first administration (Visit 1).

The pre-administration procedures for this visit will be:

- Physical examination (as at Visit 1, including ECOG performance status and disease assessment).
- Recording of (serious) adverse events and autoimmune diseases.
- Recording of pIMD.
- A pregnancy test should be performed at any time during the study for all women of child-bearing potential if the investigator or patient suspects that pregnancy has occurred while the patient was being treated on protocol therapy.

In addition:

- Before administration, the criteria for permanent stopping (Section 5.2.1.2) or postponement of study treatment (Section 5.2.1.1) will be checked; if any of these is met, the patient will

either be withdrawn from study treatment or the present administration of study treatment will be postponed. Study treatment will then be administered, provided that this is not contra-indicated by the findings of the previous 2 steps.

6.3.5. Visit 3: Third study treatment administration

This visit will take place 6 weeks \pm 4 calendar days after the day of the first treatment administration (Visit 1). Study procedures will include all those of Visit 2.

In addition:

- Blood sampling for humoral immunity assays will be done (10 ml, as described in Section 6.4.2). If the second study treatment administration had to be postponed (refer to Section 5.2.1.1 for criteria for postponement of study treatment), Visit 3 should be planned as close as possible to the 6 weeks \pm 4 calendar days after Visit 1 schedule, but a minimum of 14 days after the second treatment administration.

6.3.6. Visit 4: Fourth study treatment administration

This visit will take place 9 weeks \pm 4 calendar days after the day of the first administration (Visit 1). Study procedures will be identical to those of Visit 2.

If the third study treatment administration had to be postponed (refer to Section 5.2.1.1 for criteria for postponement of study treatment), Visit 4 should be planned as close as possible to the 9 weeks \pm 4 days after Visit 1 following the original schedule, but a minimum of 14 days after the third treatment administration.

6.3.7. Visit 5: Fifth study treatment administration

This visit will take place 12 weeks \pm 4 calendar days after the day of the first administration (Visit 1). Study procedures will be identical to those of Visit 3.

- For patients who agree, eight green tops of blood totaling 70 mL will be taken on days 1, 3, 7, 14 and 21 after the first and fifth doses of study drugs for assessment of T cell reactivity. Day 21 after the first dose of study drug would be the day of the second injection of study drug. Those assays will be performed by [REDACTED]

In addition:

- A CT scan of the neck, chest and upper abdomen and pelvic CT scans will be performed.
- Blood sampling for safety haematological and chemical assays (15 ml, as described in Section 6.4.2).
- A pregnancy test will be performed for females of childbearing potential. 6.3.8.
- Leukapheresis will be repeated.

Blood sampling for humoral immunity assays will be done (10 ml, as described in Section 6.4.2).

6.3.8. Visits 6-13: Three-monthly maintenance treatment administrations

These visits will take place at 3-month intervals, i.e., at time-points 6, 9, ..., 27 months after Visit 1, with a permitted deviation from the scheduled time-point of up to 14 calendar days.

The following procedures will be performed at each of these visits:

- Physical examination (as at Visit 1, including ECOG performance status and disease assessment).
- A CT scan of the neck, chest and upper abdomen and pelvic CT scan.
- Before administration of study treatment the criteria for permanent stopping or postponement of study treatment (Sections 5.2.1.1 and 5.2.1.2) will be checked; if any of these is met, the patient will either be withdrawn from study treatment or the administration of study treatment will be postponed.
- Recording of (serious) adverse events and pIMD.
- A pregnancy test for females of childbearing potential.
- Recording of concomitant medications.
- Administration of the study treatment.

The following procedures will be performed before the administration of study treatment at Visits 7, 8 and 10:

- Blood samples (10 ml, as described in Section 6.4.2) for humoral immunity assays will be taken.

The following procedures will be performed once every year after Visit 1 (i.e. at Visits 8 and 12):

- Blood sampling (15 ml as described in Section 6.4.2) for haematological and chemical safety assays.

If any of the sixth to twelfth study treatment administrations had to be postponed (refer to Section 5.2.1.1 for criteria for postponement of study treatment), the subsequent Visit should be planned as close as possible to the 3-monthly interval of the original schedule, but with a minimum of 14 days between any two treatment administrations.

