6.2.2. Maintenance phase

Study phase:	MAINTENANCE (V6-V13)								Concluding visit
Study visit no.	6	7	8	9	10	11	12	13	14 ^a
Study treatment administration no.	6	7	8	9	10	11	12	13	-
Weeks after 1. study treatment administration	24	36	48	60	72	84	96	108	120
Months after 1. study treatment administration	6	9	12	15	18	21	24	27	30
Efficacy assessments									
Neck, chest, abdomen and pelvic CT scans	•	b	•	b	•	b	•	b	•
Physical examination	•	•	•	•	•	•	•	•	•
Safety assessments									
Adverse events recorded	•	•	•	•	•	•	•	•	•
pIMD recorded	•	•	•	•	•	•	•	•	•
Serious adverse events recorded	•	•	•	•	•	•	•	•	•
Laboratory assays									
Blood samples taken for:									
Haematology			•				•		•
Blood chemistry			•				•		•
Humoral immunity		•	•		•				•
PBMC for cellular immune assays		•			•		•		•
Pregnancy test (for female patients) ^{c, d}	•	•	•	•	•	•	•	•	•
Investigational product									
Criteria for permanent stopping or postponement of study treatment	•	•	•	•	•	•	•	•	
Recording of concomitant medications	•	•	•	•	•	•	•	•	•
recMAGE-A3 + AS15 +/- Poly IC:LC administration	•	•	•	•	•	•	•	•	
Treatment conclusion									• ^e

As a convention, 1 month is defined as 4 weeks, i.e., 28 days, during the treatment phase.

- a. The procedures of this visit are also to be carried out in case of relapse or early withdrawal.
- b. To be repeated/performed at any time if clinically indicated.
- c. A pregnancy test must be performed every 3 months for female patients of childbearing potential.
- d. A pregnancy test should be performed at any time during the study if the investigator/patient suspects that pregnancy has occurred.
- e. After concluding visit, patients will be followed-up every 6 months until relapse or for up to 5 years from the first administration of study treatment. Refer to Table 7 for details on the follow-up phase.
- f. 10 mL of blood sample taken for examination of humoral immunity. It may also be used for translational research.
- g. Pictures should be taken document cutaneous recurrences

Table 6. Timing of study visits and the assessments to be performed (Maintenance Phase and Concluding Visit)

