6.2.3. Follow-up period

The duration of active follow-up for survival, recurrence and serious adverse events (SAEs) related to study participation and concurrent medications will be up to 5 years from the first

CONFIDENTIAL

study treatment. The procedures described in the table below will be performed for patients having completed study treatment or for patients withdrawing from treatment prior to completion for reasons other than recurrence.

After relapse, annual post-study contacts, e.g., by telephone, will be instituted to follow the patients for survival.

Study phase:	FOLLOW-UP (F1 - F n+1)					
Study visit no.	F1	F2	F3	F4	F5 to Fn ^a	Fn+1
Date of concluding visit (CV) + no. of months	CV+6m	CV+12m	CV+18m	CV+24m	CV+... ^a	60 m
Safety assessments						
pIMD recorded	•	•	•	•	•	•
Serious adverse events related to study participation and GSK concomitant medications recorded	•	•	•	•	•	•
Laboratory assays						
Blood samples taken for: Humoral immunity ^c		•				
Efficacy assessments						
Neck, chest, abdomen and pelvic CT	•	^b	•	^b	•	•
Physical examination	•	•	•	•	•	•

Months are here defined as calendar months.

- a. These visits will be started 6 months after the concluding visit (whether the patient completed the scheduled 13 injections or was withdrawn from the study treatment before completion) and will be repeated every 6 months until 5 years after first study treatment administration are reached.
- b. To be repeated at any time if clinically indicated..
- c. 10 ml of blood sample taken for examination of humoral immunity. It may also be used for optional translational research.

Table 7. Timing of study visits and the assessments to be performed (Follow-up Phase)

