6.3.10 Post-treatment follow-up

- a. For procedures of Visit 14 - concluding visit, refer to Section 6.3.9 .
 b. For 5-year follow-up of patients who have completed the treatment phase, refer to Section 6.3.10.2.
 c. For 5-year follow-up of patients who have not completed the treatment phase, refer to Section 6.3.10 2.
 d. Five-year follow-up is performed until five years after first administration or until recurrence of disease.

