6.3.10.1. Follow-up of patients who have completed the study treatment

CONFIDENTIAL

For patients who have completed the study treatment (up to and including Visit 14), follow-up visits will take place every 6 months after the concluding visit (Visit 14) for a maximum of 5 years after first study treatment administration.

The following procedures will be performed:

- A routine physical examination including assessment of ECOG performance status. Determination of disease status, on the basis of the patient's medical records and all other available information. If the patient has relapsed, the investigator will obtain information about the recurrence (date, type), as far as this is possible.
- CT scan of the neck, chest and upper abdomen as well as the pelvis (at Months 36, 48 and 60, or at any other time if clinically indicated).
- Recording of pIMD.
- Recording of SAEs related to study participation and concurrent medications.
- In addition, one year after the concluding visit, a blood sample (10 ml as described in Section 6.4) will be taken for humoral immunity testing.

Follow-up visits will be numbered consecutively from Visit F1 onwards. Findings at these visits will be recorded using Moffitt CRFs.

If relapse of disease is established at one of the follow-up visits, no further follow-up visits will take place. As for patients who have withdrawn from the study treatment (Section 6.3.10.2) because of disease relapse, annual post study contacts, e.g., by telephone, will be instituted and continued up to 5 years after the first study treatment administration.

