6.3.10.2. Follow-up of patients who were withdrawn from the study treatment

Patients will be free to withdraw from the study at any time and for any reason and without prejudice to their further treatment. However, all patients who have withdrawn from study treatment will be examined at least 30 days after the last administration of study treatment and before starting any other anti-cancer treatment. The procedures to be performed at this examination are those defined for Visit 14 (see Section 6.3.9). Note that if a CT-scan has been performed at the last administration of study treatment this will not be repeated.

In addition, all patients who have withdrawn from study treatment will be followed every 6 months after the last contact for up to 5 years from the date of first study treatment administration to document disease recurrence, survival and safety parameters (until another cancer treatment is initiated). The procedures at these examinations are the same as for patients who have completed study treatment (See Section 6.3.10.1).

For female patients withdrawing because of pregnancy or decision to become pregnant, in addition to the follow-up of the melanoma, there will be a follow-up of the pregnancy as described in Section 8.12.

There are two exceptions to this follow-up:

- a. Patients who have withdrawn from the study because of withdrawal of consent will not be contacted again.
- b. Patients who were withdrawn from study treatment because of disease relapse or who relapsed during the post-treatment study period will not be asked to return for study follow-up visits. These patients will be contacted yearly, e.g., by telephone, to follow them for survival.

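### The missed-visit sensitivity analysis of RFS can date a relapse before a later negative scan, which pulls its hazard ratio towards 1 (minor)

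*Combined protocol and SAP*

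**What the plan says.** **Dating of relapse (10.7.3.1.1).** The main RFS analysis is an adjusted Cox model. It assigns a relapse to the visit that finds it and ignores earlier missed visits. One sensitivity analysis keeps the model but changes the date: for a patient who did not keep to the evaluation schedule, the event moves to the first evaluation missed before the recurrence was found. No condition ties that visit to the last negative assessment. The section mentions interval-censored methods as a possibility and leaves further detail to a Report Analysis Plan, which is not among the documents.

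**CT calendar on treatment.** Section 6.3.8 lists, among the procedures for each of Visits 6 to 13, "A CT scan of the neck, chest and upper abdomen and pelvic CT scan". Table 6 schedules CT at Visits 6, 8, 10 and 12. Visits 7, 9, 11 and 13 carry only a footnote: "To be repeated/performed at any time if clinically indicated". No rule says which source prevails.

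**CT calendar in follow-up.** For patients who completed treatment, 6.3.10.1 sets CT "at Months 36, 48 and 60, or at any other time if clinically indicated". For patients who stopped early, 6.3.10.2 says: "The procedures at these examinations are the same as for patients who have completed study treatment (See Section 6.3.10.1". Section 6.2.3, however, applies Table 7 to completers "or for patients withdrawing from treatment prior to completion for reasons other than recurrence", and its footnote a sets the clock: "These visits will be started 6 months after the concluding visit (whether the patient completed the scheduled 13 injections or was withdrawn". Item b of 6.3.10 reads "For 5-year follow-up of patients who have completed the treatment phase, refer to Section 6.3.10.2", which is the section on withdrawn patients.

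**The concern.** A missed-visit sensitivity analysis should ask how far the result depends on relapses that might have been found sooner. A relapse found after a gap can reasonably be moved back to the start of that gap. It cannot be moved past a scan that showed no disease. The rule as worded allows this, because it takes the first miss in the patient's whole history.

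The error is also not neutral between arms. A patient who relapses late has passed more scheduled evaluations, so is more likely to have missed one early and to be pulled back a long way. The arm with longer RFS therefore loses more time, and the analysis leans towards no difference by construction. A weaker result could then be misread as a lack of robustness.

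The CT calendar matters here because the rule needs to know which evaluations were due. Visits 7, 9, 11 and 13 are CT visits under 6.3.8 and not under Table 6.

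**Working it through.** **1. The plan's RFS power (10.3).** Inputs: medians 12 and 24 months, 20 per arm, one-sided 0.05, 2.5 patients a month (40/2.5 = 16 months), then 36 months of follow-up. With exponential times, λ = ln 2/median, accrual A and follow-up F, the event probability is 1 − [exp(−λF) − exp(−λ(A+F))]/(λA), which gives 0.918 and 0.717. Expected events are 20 × (0.918 + 0.717) = 32.7. Freedman's formula gives power Φ(√32.7 × 0.5/1.5 − 1.645) = Φ(0.261) = 60.3%, against about 61% stated. The design reproduces.

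**2. One patient.** Table 6 puts Visits 6, 8 and 10 at weeks 24, 48 and 72. The patient misses Visit 6, is negative at Visit 8 and positive at Visit 10.

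| Rule | Event date |
|---|---|
| Main analysis | week 72 |
| Sensitivity rule as worded | week 24, 24 weeks before the negative scan |
| First CT missed after the last negative scan | week 72 (none missed) |

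Both calendars schedule CT at these three visits, so the example does not depend on which is followed.

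**3. How often (illustration).** The documents give no missed-visit rates. Assume that each scheduled CT is missed independently with probability q, equally in both arms. Scans fall at weeks 12, 24, 48, 72, 96 and 120 (4.348 weeks to a month), then at Months 36, 48 and 60. If n scans precede the true relapse, the event is dated before a later negative scan unless all misses among those n come last:

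P(n) = 1 − Σ (1−q)^a q^(n−a), summed over a = 0 to n.

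The share relapsing in each interval is 2^(−start/12) − 2^(−end/12) for a 12-month median. For q = 0.10:

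| Scans before relapse, n | Share of patients | P(n) |
|---|---|---|
| 0 | 0.147 | 0 |
| 1 | 0.126 | 0 |
| 2 | 0.199 | 0.090 |
| 3 | 0.144 | 0.180 |
| 4 | 0.105 | 0.262 |
| 5 | 0.076 | 0.336 |
| 6 | 0.078 | 0.402 |
| 7 | 0.062 | 0.462 |
| 8 | 0.031 | 0.516 |

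The products sum to 0.173. Dividing by the total share, 1 − 2^(−5) = 0.969, gives about 18%. The same steps give about 10% at q = 0.05 and 29% at q = 0.20. With a 24-month median the shares are about 14, 25 and 40%. The difference between the arms is the source of the bias.

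**4. Effect on the hazard ratio.** Cox model with Efron ties, 300,000 simulated patients per arm, medians 12 and 24 months, follow-up to Month 60:

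| q | As worded | Corrected rule | Dated at detection |
|---|---|---|---|
| 5% | 0.527 | 0.503 | 0.503 |
| 10% | 0.546 | 0.504 | 0.504 |
| 20% | 0.573 | 0.505 | 0.506 |

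**5. Size against precision.** With 32.7 events, SE(log HR) ≈ 2/√32.7 = 0.35. The shifts are ln(0.527/0.503) = 0.047, ln(0.546/0.504) = 0.080 and ln(0.573/0.505) = 0.126, or 0.13, 0.23 and 0.36 standard errors.

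**6. The calendars.** Section 6.3.8 gives 8 scans over Visits 6 to 13 and Table 6 gives 4. At a 12-month median the mean delay to a scan-found relapse on treatment is 1.4 months against 2.4. Simulated log-rank power for the 12 against 24 month design (40,000 trials) is 60.4% on either calendar.

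In follow-up, completers get the same scans only nominally. Treatment months are 28 days, so the concluding visit at week 120 falls at calendar month 120/4.348 = 27.6, and Table 7's scans fall at 33.6, 45.6 and 57.6, then 60. For early stoppers, a literal Month 36 first scan would leave these gaps since the last scan: after dose 5, 36 − 12/4.348 = 33.2 months; after dose 8, 36 − 48/4.348 = 25.0; after dose 10, 36 − 72/4.348 = 19.4. Each is one month shorter if CT is done at a concluding visit one month after the last dose. Under Table 7 the first scan comes 6 months after the concluding visit and no later gap exceeds 12.

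**The case against.** - **The Report Analysis Plan may settle the rule, and the sentence could mean the first miss in the run leading up to detection.** Both are possible. But the protocol promises only further detail, and its wording does not contain that limit. The correction makes the sensible reading explicit.
- **Missed visits are handled elsewhere.** Section 6.1.1 sets windows of 4 and 14 days and has the sponsor classify larger deviations. Section 5.2.1.1 asks for postponed doses to be made up promptly. These should reduce misses, and the assumed 5 to 20% ignores them. Neither defines a missed evaluation for RFS.
- **It is one sensitivity analysis of a secondary endpoint, and interval-censored methods are named.** This stands, and it sets the grade. The interval-censored analysis is only an option, so it does not repair the rule.
- **Two stronger readings are tempting.** A reader might infer that the conflicting CT calendars undermine the main RFS comparison. They do not: both arms share the calendar, relapse is dated at detection, and power is the same on either one. A reader might also infer that early stoppers go two years or more without a scheduled scan. That follows only if 6.3.10.2 is taken to carry over the months as well as the procedures. Table 7 expressly covers these patients and counts from their own concluding visit, which is the natural reading. Six-monthly physical examination and clinically indicated CT continue in any case.

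**Conclusion.** The concern holds for the sensitivity rule and is minor. As worded, the rule can place a relapse before a documented negative scan, and it pulls the hazard ratio towards 1 even with equal missing in both arms. At assumed miss rates of 5 to 20% the ratio is about 0.53 to 0.57 instead of 0.50 to 0.51, which is 0.13 to 0.36 standard errors at this trial's size.

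These figures rest on exponential relapse times, independent misses, relapse found by scan, the Table 6 calendar and the plan's assumed medians. The direction follows from the rule; the size depends on miss rates that the documents do not give. It is not established that any relapse has been misdated. The conflicts over CT timing are real but editorial.

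**What to change.** **Main change.** In 10.7.3.1.1, and in the Report Analysis Plan, replace the dating rule with: *the event is dated at the first scheduled CT missed after the last negative scan, or at detection if none was missed.* State which scans count as scheduled and when one counts as missed. Optionally, also run the interval-censored analysis on the actual last-negative and first-positive scan dates.

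**Supporting clean-up.**
- Align 6.3.8 with Table 6: CT at Visits 6, 8, 10 and 12, otherwise if clinically indicated, in both arms. Record which calendar was actually followed.
- State in 6.3.10.1 and 6.3.10.2 that relapse-free early stoppers follow Table 7 from their concluding visit.
- Point item b of 6.3.10 to 6.3.10.1.

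**Cost.** One changed derivation and a few lines of text, with no scans beyond Tables 6 and 7. This version is dated 28 October 2015. If recruitment ended by February 2013 as Appendix A planned, the last concluding visits fell between about mid-June and early September 2015, so the 6.3.8 change would mainly be a matter of record. Five-year follow-up would run to about February 2018, so the follow-up clarification could still matter, and the dating rule can be corrected before the analysis.
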